## 11.3 Methods for Evaluation of Measurable Disease

All measurements should be taken and recorded in metric notation using a ruler. All baseline evaluations should be performed as closely as possible to the beginning of treatment and never more than 2 weeks before the beginning of the treatment.

**Clinical lesions:** Clinical lesions will only be considered measurable on brain MRI when they are  $\geq 5$  mm diameter as assessed using a ruler.

**Histology:** This technique can be used to differentiate between partial responses (PR) and complete responses (CR) in rare cases when biopsy or surgical resection of a measureable lesion is clinically indicated.

**Perfusion/CBV:** This advanced brain MRI technique can be used as an adjunct test to determine treatment response or disease status. However, it should not be used as the primary or sole method to determine response or disease status.

**Brain FDG-PET coupled with head CT or brain MRI:** This advanced metabolic imaging technique can be used as an adjunct test to determine response or disease status. However it should be used as the primary or sole method of determining response or disease status.

### **11.3.1 Evaluation of Target Lesions**

**Complete Response (CR):** Disappearance of all target lesions.

**Partial Response (PR):**  $\geq 50\%$  decrease compared with baseline in the sum of products of perpendicular diameters of all target lesions sustained for at least 4 weeks.

**Progressive Disease (PD):** At least a 25% increase in the sum of products of perpendicular diameters of at least 1 target lesion, taking as reference the smallest sum of products of perpendicular diameters on study (this includes the baseline sum if that is the smallest on study). The absolute increase in any dimension must be at least 5mm when calculating the products of perpendicular diameters.

**Stable Disease (SD):** Neither sufficient shrinkage to qualify for PR nor sufficient increase to qualify for PD, taking as reference the smallest sum of products of perpendicular diameters while on study.

### **11.3.2 Evaluation of Non-Target Lesions**

**Complete Response (CR):** Disappearance of all non-target lesions.

**Non-CR/Non-PD:** Persistence of one or more non-target lesion(s).

**Progressive Disease (PD):** Appearance of one or more new lesions and/or unequivocal progression of existing non-target lesions on stable or increasing doses of corticosteroids compared with baseline scan or best response after initiation of therapy\* not caused by comorbid events (e.g. radiation therapy, demyelination, ischemic injury, infection, seizures, postoperative changes, or other treatment effects). Unequivocal progression should not normally trump target lesion status. It must be representative of overall disease status change, not a single lesion increase.

Although a clear progression of “non-target” lesions only is exceptional, the opinion of the treating physician should prevail in such circumstances, and the progression status should be confirmed at a later time by the review panel (or Principal Investigator).

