Progressive disease $\geq$ 12 weeks after chemoradiotherapy completion	
 
1. New contrast-enhancing lesion outside of radiation field on decreasing, stable, or increasing doses of corticosteroids.
 
2. Increase by <math>\geq 25\%</math> in the sum of the products of perpendicular diameters between the first postradiotherapy scan, or a subsequent scan with smaller tumor size, and the scan at 12 weeks or later on stable or increasing doses of corticosteroids.
 
3. Clinical deterioration not attributable to concurrent medication or comorbid conditions is sufficient to declare progression on current treatment but not for entry onto a clinical trial for recurrence.
 
4. For patients receiving antiangiogenic therapy, significant increase in T2/FLAIR nonenhancing lesion may also be considered progressive disease. The increased T2/FLAIR must have occurred with the patient on stable or increasing doses of corticosteroids compared with baseline scan or best response after initiation of therapy and not be a result of comorbid events (eg, effects of radiation therapy, demyelination, ischemic injury, infection, seizures, postoperative changes, or other treatment effects).
 

Criteria for Response Assessment Incorporating MRI and Clinical Factors (Adapted from JCO 2010)

Response	Criteria
Complete response	
 
• Requires all of the following: complete disappearance of all enhancing measurable and nonmeasurable disease sustained for at least 4 weeks.
 
• No new lesions; stable or improved nonenhancing (T2/FLAIR) lesions.
 

Response	Criteria
	
 
Patients must be off corticosteroids (or on physiologic replacement doses only) and stable or improved clinically. Note: Patients with nonmeasurable disease only cannot have a complete response; the best response possible is stable disease.
 

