## 11.2 Disease Parameters

**Measurable disease:** Bi-dimensionally measurable lesions with clearly defined margins by MRI scan. All tumor measurements must be recorded in millimeters (or decimal fractions of centimeters).

**Non-measurable or evaluable disease:** Uni-dimensionally measurable lesions or lesions with margins not clearly defined such as areas of T2/FLAIR signal abnormality or poorly defined enhancing abnormality.

Note: For cystic lesions, the only measurable part is any enhancement area around the cyst that is clearly defined and bi-dimensionally measurable. The cyst itself should not be considered measurable or non-measurable disease.

**Target lesions:** All measurable lesions that are residual of the lesion treated with MLA should be identified as target lesions and recorded and measured. Target lesions should be selected on the basis of their size (lesions with the longest diameter), but in addition should be those that lend themselves to reproducible repeated measurements. It may be the case that, on occasion, the largest lesion does not lend itself to reproducible measurement in which circumstance the next largest lesion, which can be measured reproducibly should be selected. When there are too many measurable lesions, choose the largest three lesions as target lesions to follow. The other measurable lesions should be considered evaluable for the purpose of objective status determination.

**Non-target lesions:** All non-measurable lesions should be identified as non-target lesions and should also be recorded at baseline. Measurements of these lesions are not required, but the presence, absence, or in rare cases unequivocal progression of each should be noted throughout follow-up.

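### Section 11.3.2 requires T2/FLAIR abnormality to disappear for non-target CR, while 11.1 and the RANO summary in 11.3.3 require only that it be stable or smaller, and no section says which rule prevails

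*Combined protocol and SAP*

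**What the plan says.** Four places in Section 11 bear on CR.

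- **11.2 Disease Parameters.** Non-measurable disease includes "lesions with margins not clearly defined such as areas of T2/FLAIR signal abnormality". The same section adds: "All non-measurable lesions should be identified as non-target lesions". It makes no exception for nonenhancing signal.
- **11.3.2 Evaluation of Non-Target Lesions.** CR is "Disappearance of all non-target lesions". If even one persists, the category is Non-CR/Non-PD.
- **11.1 Antitumor Effect.** CR needs "complete disappearance of all enhancing measurable and nonmeasurable disease sustained for at least 4 weeks". For the rest of the scan it needs "No new lesions; stable or improved nonenhancing (T2/FLAIR) lesions". The patient must also be off corticosteroids (physiologic replacement is allowed) and clinically stable or improved. Patients with only nonmeasurable disease cannot be CR.
- **11.3.3 Evaluation of Best Overall Response.** In the RANO summary table, the CR column has no enhancing disease and T2/FLAIR stable or decreased, with all criteria required.

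Section 11.1 names RANO as the criteria for response and progression, and 13.2.1 analyses duration of response according to RANO.

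**The concern.** The two sets of rules treat the same finding differently. In 11.1, the disease that must vanish is limited to enhancing disease, and nonenhancing T2/FLAIR change has its own, weaker condition. In 11.2 and 11.3.2 that limit is lost: T2/FLAIR abnormality enters the non-target group, and the whole group must vanish.

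No section says how the target rating (11.3.1) and the non-target rating (11.3.2) combine into an overall response, or which rule prevails if they disagree with 11.3.3. Two assessors following the protocol in good faith could record different best responses for one patient. Best overall response (11.3.3) and the duration of overall CR (11.3.4) are defined from these categories, and secondary endpoint 5 (13.1.2) relates sleep pattern to response to treatment.

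**Working it through.** No sample size, power or error rate is involved, and the plan states no figure to reproduce. The check is to apply each rule to one test patient.

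**Test patient.** Measurable enhancing tumour at baseline, now gone for at least 4 weeks; no new lesion; off corticosteroids; clinically stable; T2/FLAIR abnormality present at baseline and unchanged.

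| Rule | Requirement for T2/FLAIR | Result |
|---|---|---|
| 11.1, CR definition | stable or improved | CR |
| 11.3.3, RANO summary | stable or decreased | CR |
| 11.2 with 11.3.2 | must disappear, as a non-target lesion | Non-CR/Non-PD for non-target disease |

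**Where the rules agree.** They give the same answer if T2/FLAIR abnormality was absent at baseline or has disappeared. They also agree on poorly defined enhancing abnormality, which 11.2 likewise calls non-measurable: all require it to go. The conflict is confined to persisting nonenhancing signal that is stable or improved.

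**Is T2/FLAIR really meant to fall under 11.3.2?** The wording of 11.2 puts it there. The progression paragraph of 11.3.2 points the same way: its corticosteroid condition, its reference to baseline or best response and its list of excluded comorbid events closely follow the T2/FLAIR progression item in 11.1.

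**What changes downstream.**

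1. *Best overall response.* If 11.3.2 is applied, the test patient is not CR. The patient still meets the 11.1 conditions for partial response: at least a 50% decrease sustained for 4 weeks, no progression of nonmeasurable disease, stable T2/FLAIR, no corticosteroid increase, clinically stable. CR and PR combined is therefore unchanged.
2. *Duration of overall response.* Under 11.3.4 it starts at CR or PR, whichever is recorded first, and ends at progression. Neither date depends on the CR/PR label here.
3. *Duration of overall CR.* Under 11.3.4 it starts when the measurement criteria for CR are first met, so it can depend on which CR rule the assessor uses.
4. *Secondary endpoint 5.* It is affected only if response category is the response variable.
5. *Primary endpoint, PFS, OS.* These rest on dosing-time compliance, on progression or death, and on death. None uses CR.

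**Scale.** With the planned 40 patients, each reclassified patient moves a CR proportion by 1/40 = 2.5 percentage points. This is a unit, not an estimate: the documents give neither a CR rate nor a rate of residual T2/FLAIR signal.

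**The case against.** The strongest reply is that 11.3.2 rates one lesion category and does not assign overall response. Non-CR/Non-PD is not among the four overall categories in 11.3.3. The only table under best overall response is the RANO summary, and 11.1 and 13.2.1 also name RANO. On this reading RANO decides, and the mismatch is editorial.

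Much of this stands. It shows which rule was probably intended and keeps the point minor. It does not make the text consistent: no sentence gives 11.1 or 11.3.3 precedence, and if 11.3.2 does not feed overall response, its CR category has no stated use. Section 11.3.3 also makes best response depend on measurement and confirmation criteria, so an assessor can reasonably take the lesion-level rules as part of them.

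The reply is also right that little in the planned analysis rests on CR. CR rate is not an endpoint in 13.1. The correlation variables listed in 13.2.1 include tumor size but no response category. Section 13.2 plans no separate analysis of duration of CR.

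Four stronger readings are tempting but unsupported:

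- *Every patient who loses all enhancement but keeps T2/FLAIR signal changes category.* Not so. A patient who is still on more than replacement corticosteroids, has declined clinically, has a new lesion, has not held the response for 4 weeks, has increasing T2/FLAIR or had only nonmeasurable disease is not CR under 11.1 either.
- *CR percentages can be compared under the two rules.* Any such figures would rest on assumed rates with no anchor in the documents.
- *Under the non-target rule the CR duration never starts.* Section 11.3.4 ties the start to measurement criteria, and 11.2 does not require non-target lesions to be measured, so the text does not settle this.
- *Unblinded reading lets the assessor choose the category.* Sections 4.4 and 5.1 imply that patients know their assigned dosing time, but no section says whether the image readers do.

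**Conclusion.** The inconsistency is real and follows from the text without any assumption. It concerns patients who meet every other RANO condition for CR and have persisting T2/FLAIR signal that is stable or improved. For them it can change best response from CR to a lesser category, alter the recorded duration of overall CR, and carry into secondary endpoint 5 if response category is used there.

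Its weight is low. This is a descriptive 40-patient feasibility study whose primary endpoint, PFS and OS are untouched, and duration of overall response is essentially unchanged where measurable disease was present. The number of patients affected cannot be estimated from the documents. The reason to act is that a stated response rule contradicts the criteria the protocol itself adopts, and the repair is simple.

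**What to change.** Make four wording changes, using the rule already in 11.1:

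1. In 11.3.2, reword the CR line to: *Disappearance of all enhancing non-target lesions, with nonenhancing (T2/FLAIR) lesions stable or improved.*
2. In 11.3.2, make the Non-CR/Non-PD line refer to persistence of one or more enhancing non-target lesions.
3. In 11.2, list T2/FLAIR abnormality separately from enhancing non-measurable lesions.
4. In 11.3.3, state that overall response is assigned by the RANO criteria in 11.1 and 11.3.3.

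When making the third change, confirm that the progression line of 11.3.2 still reads correctly for T2/FLAIR. Sections 11.1 and 11.3.3 already count a T2/FLAIR increase as progression, so the PFS definition need not change.

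The cost is a text amendment. It needs no extra scans, readers or patients. Any CR status already recorded in patients with residual T2/FLAIR signal should be checked once against the clarified rule.

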### 11.3.3 Evaluation of Best Overall Response

The best overall response is the best response recorded from the start of the treatment until disease progression/recurrence (taking as reference for progressive disease the smallest measurements recorded since the treatment started). The patient's best response assignment will depend on the achievement of both measurement and confirmation criteria.

Summary of the RANO Response Criteria (Adapted from JCO 2010)

Criterion	CR	PR	SD	PD
T1 gadolinium enhancing disease	None	$\geq 50\% \downarrow$	$< 50\% \downarrow$ but $< 25\% \uparrow$	$\geq 25\% \uparrow^*$
T2/FLAIR	Stable or $\downarrow$	Stable or $\downarrow$	Stable or $\downarrow$	$\uparrow^*$
New lesion	None	None	None	Present*
Corticosteroids	None	Stable or $\downarrow$	Stable or $\downarrow$	NA†
Clinical status	Stable or $\uparrow$	Stable or $\uparrow$	Stable or $\uparrow$	$\downarrow^*$
Requirement for response	All	All	All	Any*

Abbreviations: RANO, Response Assessment in Neuro-Oncology; CR, complete response; PR, partial response; SD, stable disease; PD, progressive disease; FLAIR, fluid-attenuated inversion recovery; NA, not applicable.

\* Progression occurs when this criterion is present.

† Increase in corticosteroids alone will not be taken into account in determining progression in the absence of persistent clinical deterioration.

### 11.3.4 Duration of Response

**Duration of overall response:** The duration of overall response is measured from the time measurement criteria are met for CR or PR (whichever is first recorded) until the first date that recurrent or progressive disease is objectively documented (taking as reference for progressive disease the smallest measurements recorded since the treatment started).

The duration of overall CR is measured from the time measurement criteria are first met for CR until the first date that progressive disease is objectively documented.

**Duration of stable disease:** Stable disease is measured from the start of the treatment until the criteria for progression are met, taking as reference the smallest measurements recorded since the treatment started, including the baseline measurements.

### **11.3.5 Neurological Exam and Performance Status**

Patients will be graded using the Karnofsky Performance Status scale and their neurological function evaluated as improved, stable or deteriorated in addition to objective measurement of tumor size. These parameters will be used to determine the overall response assessment.

### **11.3.6 Progression-Free Survival**

PFS is defined as the duration of time from start of treatment to time of progression or death, whichever occurs first.

## **12.0 DATA AND SAFETY MONITORING**

In compliance with the Washington University Institutional Data and Safety Monitoring Plan, the Principal Investigator will provide a Data and Safety Monitoring (DSM) report to the Washington University Quality Assurance and Safety Monitoring Committee (QASMC) semi-annually beginning six months after accrual has opened (if at least five patients have been enrolled) or one year after accrual has opened (if fewer than five patients have been enrolled at the six-month mark).

The Principal Investigator will review all patient data at least every six months, and provide a semi-annual report to the QASMC. This report will include:

- HRPO protocol number, protocol title, Principal Investigator name, data coordinator name, regulatory coordinator name, and statistician
- Date of initial HRPO approval, date of most recent consent HRPO approval/revision, date of HRPO expiration, date of most recent QASMC audit, study status, and phase of study
- History of study including summary of substantive amendments; summary of accrual suspensions including start/stop dates and reason; and summary of protocol exceptions, error, or breach of confidentiality including start/stop dates and reason
- Study-wide target accrual and study-wide actual accrual
- Protocol activation date
- Average rate of accrual observed in year 1, year 2, and subsequent years
- Expected accrual end date and accrual by cohort
- Objectives of protocol with supporting data and list the number of participants who have met each objective
- Measures of efficacy
- Early stopping rules with supporting data and list the number of participants who have met the early stopping rules
- Summary of toxicities separated by cohorts
- Abstract submissions/publications
- Summary of any recent literature that may affect the safety or ethics of the study

The study principal investigator and Research Patient Coordinator will monitor for serious toxicities on an ongoing basis. Once the principal investigator or Research Patient Coordinator

becomes aware of an adverse event, the AE will be reported to the HRPO and QASMC according to institutional guidelines.

## **13.0 STATISTICAL CONSIDERATIONS**

This study will include 40 patients with high grade glioma (WHO grades III or IV). Based on an extensive simulation regarding the sample size for translational and pilot studies, Piantadosi (2005) recommended that a sample size of 10 to 20 patients would provide a reasonable precision for estimating preliminary information. We therefore expect that the proposed sample size for this study will be adequate in estimating both safety and preliminary efficacy data.

### **13.1 Endpoints**

#### **13.1.1 Primary Endpoint**

The feasibility of patient compliance to chronotherapy in HGG patients treated with TMZ will be the primary endpoint. Feasibility is defined as at least 80% overall compliance (8 of 10 patients) with assigned administration time. Compliance is defined as no more than one of five doses of temozolamide per cycle taken outside of the assigned administration time.

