### **2.1 Primary Objective**

To determine the feasibility of treatment compliance and randomization of HGG patients to receive temozolomide between morning (before 10:00) or evening (after 20:00) treatment groups. Feasibility is defined as at least 80% compliance with assigned administration time.

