#### **4.4 Randomization**

Eligible patients will be randomized on a 1:1 basis to receive temozolomide at one of two time points: before 10:00 or after 20:00. A computer-generated randomization scheme is used to assign subjects. It is maintained centrally by the study statistician.

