## **13.2 Data Analysis**

### **13.2.1 General Considerations**

All data will be evaluated as observed, and no imputation method for missing values will be used. All data will be presented in a descriptive manner. Each cohort will be analyzed separately, and no multiplicity adjustment across cohorts will be

performed. All other analyses are considered as exploratory, even if statistical tests are used.

Descriptive statistics will be used to summarize the trial results, i.e., statistics for continuous variables may include means, medians, ranges and appropriate measures of variability. Qualitative variables will be summarized by counts and percentages. The uncertainty of estimates will be assessed by confidence intervals. Unless otherwise specified, the calculation of proportions will be based on the sample size of the population of interest. Counts of missing observations will be included in the denominator and presented as a separate category if not otherwise specified in the statistical analysis plan (SAP).

Duration of response, according to RANO, will be calculated for each subject and will be analyzed using the Kaplan-Meier method in the primary cohorts separately.

PFS will be presented in subject listings and analyzed using the Kaplan-Meier method in the primary cohorts separately.

Correlation analysis (significance at  $R^2 \geq 0.8$ ) and slope analysis (Fisher's Exact Test) of dependent variables (naps/day, nap duration, sleep duration, % activity during waking, % activity during sleep, chronotype, chronotype variability) and independent variables (tumor grade, time since TMZ administration, time of day of TMZ administration, time since diagnosis date, tumor size, immune health) will be carried out. Each variable will be calculated daily and averaged over the collection period. Daily calculation reveals stability, while the average reveals variability.

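### The 80% feasibility criterion is a single overall figure with no requirement in each arm, so the trial could be declared feasible with one dosing window kept by only 60% of its patients

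*Combined protocol and SAP*

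**What the plan says.** Section 2.1 makes it the main aim to learn whether patients can be randomised to, and will keep, either a morning window (before 10:00) or an evening one (after 20:00). It then gives the threshold: "Feasibility is defined as at least 80% compliance with assigned administration time". Section 13.1.1 restates it with an added word and an illustration: "Feasibility is defined as at least 80% overall compliance (8 of 10 patients) with assigned administration time". The same section defines compliance for a patient: "Compliance is defined as no more than one of five doses of temozolamide per cycle taken outside of the assigned administration time".

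Section 4.4 says "Eligible patients will be randomized on a 1:1 basis", and section 13.0 plans 40 patients. The size is supported by a citation that "recommended that a sample size of 10 to 20 patients would provide a reasonable precision for estimating preliminary information"; no target precision, error rate or reference compliance rate is given.

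Section 13.2.1 says "Each cohort will be analyzed separately", but cohort is not defined. In section 13.1.2, secondary endpoints 1, 2 and 5 refer to each group or to morning and evening. The primary endpoint names no arm.

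**The concern.** The question is whether patients can be randomised to either clock window and keep it. A single overall rate does not answer that for each window, because good adherence in the easier window offsets poor adherence in the other.

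The loss would fall on the later study. Section 2.0 says this trial collects pilot data for future chronotherapy studies in glioma, and a morning-versus-evening comparison needs both windows to be kept. Under section 5.1, a dose missed at its assigned time is generally taken later rather than omitted, so non-compliance largely means dosing outside the window. If this is concentrated in one arm, the timing contrast shrinks and adherence differs by arm. A feasibility trial should detect that pattern, and an overall rule can pass in spite of it.

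**Working it through.** **Inputs.** Threshold 80%, illustrated as 8 of 10 (13.1.1). N = 40 (13.0). Allocation 1:1 (4.4), taken as exactly 20 per arm. All 40 patients are assumed evaluable; section 5.4 requires one full cycle. The true compliance rates below are assumptions, because the documents give none.

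**The plan's own figure.** 8/10 = 80%, so the percentage and the count agree. The same threshold is 0.80 × 40 = 32 patients over the whole trial, or 0.80 × 20 = 16 in one arm. The illustrated denominator of 10 is neither 40 nor 20.

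**Lowest arm compatible with a pooled pass.** With 20 per arm, the weaker arm needs at least 32 − 20 = 12 compliant patients. So 20/20 + 12/20 = 32/40 = 80%, with the weaker arm at 12/20 = 60%. The exact (Clopper-Pearson) 95% interval for 12/20 is 36% to 81%. If chance gave a 24/16 split, 24/24 + 8/16 = 32/40 would pass with the smaller arm at 50%.

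**Probabilities.** Let A ~ Binomial(20, pA) and B ~ Binomial(20, pB), independent.
- Pooled rule: P(A + B ≥ 32), summed over all pairs (A, B).
- Per-arm rule: P(A ≥ 16) × P(B ≥ 16).
- Pooled pass with an arm observed below 80%: P(A + B ≥ 32 and min(A, B) ≤ 15). If both arms reach 16 the pooled rule is met automatically, so this equals the first probability minus the second.

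Example at 95% and 65%: P(A ≥ 16) = 0.997 and P(B ≥ 16) = 0.118, so the per-arm rule passes with probability 0.997 × 0.118 = 0.118. The pooled rule passes with probability 0.595. The difference is 0.595 − 0.118 = 0.477.

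| Assumed true rates | Pooled rule passes | Both arms reach 16/20 | Pooled pass with an arm below 80% |
|---|---|---|---|
| 100% / 60% | 0.60 | 0.05 | 0.54 |
| 95% / 65% | 0.60 | 0.12 | 0.48 |
| 95% / 70% | 0.75 | 0.24 | 0.52 |
| 90% / 70% | 0.59 | 0.23 | 0.37 |
| 80% / 80% | 0.59 | 0.40 | 0.20 |
| 85% / 85% | 0.86 | 0.69 | 0.18 |
| 90% / 90% | 0.98 | 0.92 | 0.07 |

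The first four rows show what the pooled rule lets through. The last three show what a hard rule in each arm costs when the arms do not differ.

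**The case against.** **Pooling is not stated.** A reader might infer that the protocol expressly combines the arms. It does not. *Overall* could mean over doses or cycles, since the next sentence defines compliance per cycle. Section 2.1 omits the word, and 8 of 10 does not confirm a pooled count of 40. This stands: pooling is an inference. It is the natural one, because the parenthesis counts patients, the dose rule has its own sentence, and the secondary endpoints name the arms where by-arm results are wanted. On any of these readings, no arm-level requirement is written.

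**By-arm results may already be planned.** A reader might also infer that a poorly compliant arm would go unseen. The documents do not support that. The only study groups described are the morning and evening arms, so separate analysis by cohort, with the percentages and confidence intervals promised in 13.2.1, may well show each arm's compliance. This stands as to description. It does not change the criterion in 13.1.1, and nothing says which result decides if the arms disagree.

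**The study is exploratory.** No stop or go decision is tied to the 80%, and nothing in the documents predicts a 30- to 40-point gap between arms. Both are correct and limit the weight of the point. Feasibility is nevertheless the primary endpoint, and 80% is the only criterion for concluding it.

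**A per-arm rule has a price.** With 20 patients per arm and true compliance of 85% in both, requiring 16/20 in each fails with probability 1 − 0.69 = 0.31. This stands and shapes the fix.

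**Conclusion.** The point holds in a limited form. The feasibility criterion carries no arm-level requirement, although the objective concerns both windows. On the natural pooled reading it can be met with one arm at 60%. At assumed true rates of 95% and 65% it is met with probability 0.60, and with probability 0.48 it is met while an arm is observed below 80%. These figures rest on 20 evaluable patients per arm, independent outcomes and the assumed rates; they are not predictions for this trial.

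The documents do not support saying that the plan explicitly pools the arms, that by-arm compliance will go unreported, or that either window is expected to be poorly kept. This should be corrected because the change is cheap and concerns the primary endpoint, but it does not invalidate the trial.

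**What to change.** In sections 2.1 and 13.1.1, base the feasibility conclusion on compliance in each randomised arm. Replace the 8-of-10 illustration with the actual denominator. Report each arm's compliance proportion with an exact 95% interval and the difference between arms, and keep the pooled rate as supportive. In 13.2.1, define cohort.

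For the decision itself, choose one of two forms and write it down:

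1. Require at least 80% observed compliance in each arm (16 of 20 if 20 are evaluable).
2. Keep the pooled 80% threshold, and state that feasibility of both windows will not be concluded from the pooled rate alone when either arm falls below a pre-stated level.

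**Cost.** The change is wording only; the medication diary in section 5.1 already records dosing times. Option 1 is stricter and the plan should say so: with equal true rates it passes with probability 0.92 against 0.98 pooled at 90%, 0.69 against 0.86 at 85%, and 0.40 against 0.59 at 80%. Option 2 is less severe if its arm-level limit is set below 80%, but that limit must be fixed before compliance is examined by arm. If a per-arm rule was always intended, the edit only makes it explicit.
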